6.1. Safety endpoints

- Adverse reactions: Adverse events determined to be related to Lyrica by the investigator or the sponsor
- Adverse events: All-causality adverse events
- Serious adverse reactions or adverse events: Adverse reactions or adverse events determined to be serious by the investigator or the sponsor
- Major investigation items:

- Peripheral edema and edema-related events*
*: Adverse events of the cardiovascular and respiratory systems will also be checked.
- Dizziness, somnolence, loss of consciousness, syncope, and potential for accidental injury
- Vision-related events

Events to be handled as major investigation items are defined as events of safety specification in the European risk management plan of Lyrica (important identified risk: peripheral edema and edema-related events; dizziness, somnolence, loss of consciousness, syncope, and potential for accidental injury; vision-related events).

- Accident-related events:

Accident-related events are defined as events coded to the MedDRA SMQ “accidents and injuries”. These events will be evaluated for adverse events.

- Pancreas-related events:

Pancreas-related events are defined as events coded to the MedDRA SMQ “acute pancreatitis (narrow scope)”, those coded to the MedDRA HLG “exocrine pancreas conditions” or the MedDRA HLT “pancreatic neoplasms malignant (excl islet cell and carcinoid)”, and those related to the laboratory test results of primary pancreatic parameters of serum amylase, lipase, and trypsin among those coded to the MedDRA SOC “Investigations”.

- Thyroidal function-related events:

Thyroidal function-related events are defined as events coded to the MedDRA SMQ “thyroid dysfunction”.

- Change in appetite and activity-related events

Change in appetite and activity-related events are defined as events coded to the MedDRA PT “decreased activity”, “decreased appetite”, “increased appetite”, or “hypokinesia”.

- Euphoric mood-related events:

Euphoric mood-related events are defined as events coded to the MedDRA PT “euphoric mood”.

- Suicide-related events:

Suicide-related events are defined as events coded to the MedDRA SMQ “suicide/self-injury”. These events will also be evaluated for adverse events.

- Withdrawal symptom and rebound phenomenon-related events:

Withdrawal symptom and rebound phenomenon-related events are defined as events reported in patients with clinical findings at the completion of treatment of “yes” or events with the verbatim term of “withdrawal symptom and rebound phenomenon” reported.

Final identification of these events will be based on other background information available from patients experiencing the event.

- Skin disorder-related events:

Skin disorder-related events are defined as events coded to the MedDRA SOC “Skin and subcutaneous tissue disorders”.

- Body weight
- Laboratory parameters:
 - Serum creatinine, serum amylase, serum total thyroxine (T4), thyroid-stimulating hormone (TSH), fasting blood glucose, HbA1c

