2.1. Study design

Study population

- *Indication: Neuropathic pain*
- *Dosage and administration: The usual starting dose in adults is 150 mg/day of pregabalin orally administered in 2 divided doses, which may be gradually increased to 300 mg/day over one week or longer. The dose may be adjusted depending on age and symptoms as appropriate, provided the daily dose may not exceed 600 mg and Lyrica should be orally administered in 2 divided doses regardless of the daily dose.*
- *Study population: The survey covers the patients satisfying all of the following requirements:*
 - *Patients who are registered in the drug use investigation of Lyrica and are still on treatment with Lyrica after Week 13*

Observation period

The observation period of this survey will occur in succession to the 13-week observation period of the drug use investigation. It will start from Week 14 and last until Week 104 (Day 728 from the start of treatment counted as Day 1). However, in cases where treatment has been completed or discontinued before Week 104, observation will continued until completion (discontinuation) of treatment, and follow-up will be made for one week (7 days) after completion (discontinuation) of treatment.

During this survey, safety will be evaluated on the day of the first visit after Week 26, Week 52, Week 78, and Week 104 (including the last day of each observation period), as a rule. In cases where treatment has been completed or discontinued, safety will be evaluated until the day of the first visit following 7-day period after the completion (discontinuation) of treatment, and safety information will be collected for this period.

Completion of treatment means cases where further treatment with Lyrica is judged unnecessary because of achievement of the purpose of treatment set at the start of treatment (e.g., cure of target diseases).

During the observation period, the survey forms will be collected at Week 26, Week 52, Week 78, and Week 104.

Planned survey period

Survey period : April 2011 to April 2017
Registration period : April 2011 to August 2016

Target sample size and rationale

The target sample size is 310 patients who have been treated for at least 52 weeks and for 104 weeks at most.

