6.2. Efficacy endpoints

- Clinical efficacy: Efficacy of Lyrica at Week 104 (or at discontinuation/completion of treatment) will be assessed relative to baseline (including the day of start of treatment).
- Pain score: Patients are asked to rate their pain in the last 24 hours at the time of awakening on an 11-point scale from 0 (no pain) to 10 (worst possible pain).
- Sleep interference score: Patients are asked to rate their intensity of sleep interference in the last 24 hours at the time of awakening on an 11-point scale from 0 (pain does not interfere with sleep) to 10 (pain completely interferes with sleep [could not sleep because of pain]).
- Patients’ global impression of change (PGIC): Patients are asked to rate their impression relative to baseline on a 7-point scale from 1 (greatly improved) to 7 (greatly worsened).
1 = greatly improved, 2 = improved, 3 = slightly improved, 4 = unchanged
5 = slightly worsened, 6 = worsened, 7 = greatly worsened
- Clinical global impression of change (CGIC): Investigators rate their impression relative to baseline on a 7-point scale from 1 (greatly improved) to 7 (greatly worsened).
1 = greatly improved, 2 = improved, 3 = slightly improved, 4 = unchanged
5 = slightly worsened, 6 = worsened, 7 = greatly worsened

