For “peripheral edema and edema-related events”, number and proportion of patients with events will be tabulated by presence or absence of weight increase. Two types of definitions of patients with weight increase are used: 1) those with “weight increased (MedDRA PT)” reported as an adverse reaction; 2) those with body weight increased by 7% or more from baseline at least once. Number and proportion of patients with adverse reactions will be tabulated for each SOC and PT by presence or absence of peripheral edema. In addition, number and proportion of patients with the following adverse reactions will be tabulated by presence or absence of peripheral edema to evaluate the relationship between peripheral edema and cardiovascular and respiratory events.

^a: Occurrence of cardiovascular and respiratory events will be examined in patients with peripheral edema and edema-related events.

- Events coded to the MedDRA PT “arrhythmia”, “atrial fibrillation”, “cardiovascular disorder”, “cardiac failure congestive”, “hypertension”, “hypotension”, “palpitations”, “tachycardia”, or “dyspnoea”
 - Events coded to the MedDRA SOC “Cardiac disorders”, “Vascular disorders”, or “Respiratory, thoracic and mediastinal disorders”
- **Pancreas-related events, thyroidal function-related events, change in appetite and activity-related events, suicide-related events, withdrawal symptom and rebound phenomenon-related events, and skin disorder-related events**

Number and proportion of patients will be calculated for each event.

- **Patients with special background**

Number and proportion of patients with adverse reactions and serious adverse reactions will be calculated by SOC and PT in the following subgroups and other patients.

- Elderly patients
- Pediatric patients
- Patients with renal impairment
- Patients with hepatic impairment

Patients with renal impairment are defined as those with “Renal impairment: yes” or creatinine clearance of less than 60 mL/min.

- **Relationship between dosage and administration and development of adverse reactions**

In order to evaluate the relationship between dosage and administration and development of adverse reactions, number and proportion of patients with adverse reactions will be tabulated by SOC and PT for patients whose creatinine clearance and the initial daily dosage are ≥ 60 mL/min and 150 mg, respectively, and patients whose creatinine clearance and the initial daily dosage are ≥ 30 to < 60 mL/min and 75 mg, respectively.

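### Withdrawal and rebound events are selected by a finding at completion of treatment, which the SAP defines as reaching the treatment goal, so events in patients who discontinue can go uncounted

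*SAP*

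**What the plan says.** SAP Section 6.1 gives withdrawal and rebound its own event group, with two ways in. An event belongs if it meets the first route, "defined as events reported in patients with clinical findings at the completion of treatment of" yes, "or events with the verbatim term of" one fixed phrase that names withdrawal and rebound. A review step follows: "Final identification of these events will be based on other background information available from patients experiencing the event".

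Section 2.1 gives *completion* a narrow meaning: "Completion of treatment means cases where further treatment with Lyrica is judged unnecessary because of achievement of the purpose of treatment". Discontinuation is a separate outcome. Both kinds of stopping are observed afterwards: "follow-up will be made for one week (7 days) after completion (discontinuation) of treatment".

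Section 8.2.3.1, which covers adverse reactions, lists "withdrawal symptom and rebound phenomenon-related events, and skin disorder-related events" among the groups to be tabulated. The output is simple: "Number and proportion of patients will be calculated for each event".

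**The concern.** The first route uses a word that the SAP itself reserves for treatment success. On that meaning, a patient who stops for an adverse event, for lack of effect or for any other reason cannot enter by it. Only the second route is left, and it requires the reporter to have used one particular phrase. A site that records insomnia, nausea or headache a few days after the last dose has not used it.

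The first route also selects patients and then takes their events. It does not require onset after the last dose, so a yes on the form makes every reported event in that patient a candidate, including one from early treatment.

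Withdrawal and rebound is a named safety endpoint, to be reported as a number and proportion of patients in the final analysis for reexamination (Section 3). If the count is low, a reader could not tell whether the drug or the selection rule is the reason.

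**Working it through.** The SAP gives no figure for this endpoint, so there is nothing to reproduce. Its one design calculation, 310 patients for a 95% chance of seeing a reaction with 0.97% incidence, does hold: 1 − (1 − 0.0097)^310 = 0.951. It has no bearing on how these events are selected. The check is therefore a comparison of sections.

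**1. Does the SAP use completion to mean any stop?** Not elsewhere. Section 2.1 names both terms for the follow-up period. Section 6.2 does so for clinical efficacy: "Efficacy of Lyrica at Week 104 (or at discontinuation/completion of treatment) will be assessed relative to baseline". Sections 8.2.4.2, 8.2.4.3 and 8.2.4.6 also name both for the pain and sleep scores. The withdrawal definition in Section 6.1 names completion alone.

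**2. What happens to an event three days after the last dose, reported under a symptom name?**
- Completer marked yes: selected by the first route.
- Patient who discontinued, with completion read as in Section 2.1: not selected, because the first route does not apply and the phrase is absent.
- Patient who discontinued and is marked yes, if the form item is filled in at any end of treatment: selected by the first route.

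**3. What happens to an event in Week 2, on treatment, in a patient later marked yes?** It becomes a candidate, since no window excludes it. Two filters remain. One is the final review. The other is the relatedness judgement, because Section 8.2.3.1 tabulates adverse reactions and Section 6.1 defines those as events judged related to Lyrica.

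**4. Can the review repair step 2?** As written, no. It concerns the events already selected, so it can remove candidates but cannot add any. Section 6.1 states no criteria for it.

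**5. Size.** Write the missed share of true cases as d × s × u:
- d is the share of cases that occur in patients who discontinue.
- s is the share of those reported without the fixed phrase.
- u is 1 if the form item is limited to completers, and 0 if it covers every stop and the affected patients are marked yes.

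The SAP gives none of the three. With u = 0 the result is 0 whatever d and s are.

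**The case against.** The strongest objection is that the rule depends on a survey-form item that is not shown. If sites fill it in whenever treatment ends, the first route reaches patients who discontinue, and the fault is only loose wording. This stands. It means the documents show an inconsistency that can cause loss, not a loss that must occur.

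Three stronger readings are tempting, and the documents do not support them.

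- *Withdrawal events in patients who discontinue are lost.* The verbatim route is open to any patient, and the form item may be too. An event that escapes this group also still appears in the SOC and PT tables of adverse events (Section 8.2.3.2), in those of adverse reactions if judged related (Section 8.2.3.1), and in the listings (Section 9). What is at risk is the completeness of one grouped count.
- *Unrelated on-treatment events in completers are counted.* Only patients marked yes are flagged, their events are candidates, and the review and the relatedness filter both come before the tabulated number.
- *Roughly half or more of the cases go missing.* Assuming d of 60% to 80%, s of 70% to 90% and u = 1 gives 0.60 × 0.70 = 0.42 to 0.80 × 0.90 = 0.72. All of these inputs are assumptions. The figure also assumes equal risk in both groups of stoppers and full capture in completers. With u unknown, the range starts at 0.

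It is also fair to say that this endpoint is not one of the three major investigation items and that testing in the survey is exploratory. That limits the consequence but leaves the selection rule unclear.

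**Conclusion.** The point holds as a defect in the selection rule. Read with the SAP's own definition of completion, Section 6.1 can miss withdrawal events in patients who discontinue when these are reported under a symptom name. The later review cannot bring them back. The first route also lacks an onset window, so it relies on the review and the relatedness judgement to remove on-treatment events.

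The size of any undercount cannot be derived from the SAP, and it may be zero. The conclusion rests on taking completion in Section 6.1 in the sense of Section 2.1, which the paired wording elsewhere supports but the unseen form could overturn. Even then the two sections would disagree and the missing window would remain. The change is worth making because it is cheap and removes a possible undercount of a named safety endpoint.

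**What to change.** In Section 6.1:

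1. Reconcile the term with Section 2.1 by stating that the clinical-findings item applies to completion or discontinuation.
2. Define candidate events as adverse reactions with onset after the last dose, through the end of post-treatment follow-up, in all patients who stopped. Name the end of that window, since Section 2.1 mentions both the 7 days and the first visit after them.
3. Keep events with the verbatim phrase as candidates.
4. Limit events selected through the yes item to the same window.
5. Keep the final-identification review. A sentence on its criteria would help, as none are given.

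The cost is SAP wording and a programmed filter. The dates are already in use: the day of last dose in Section 8.2.2 and the days to onset in Section 8.2.3.1. The downside is more candidate events to review.

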6.2. Efficacy endpoints

- Clinical efficacy: Efficacy of Lyrica at Week 104 (or at discontinuation/completion of treatment) will be assessed relative to baseline (including the day of start of treatment).
- Pain score: Patients are asked to rate their pain in the last 24 hours at the time of awakening on an 11-point scale from 0 (no pain) to 10 (worst possible pain).
- Sleep interference score: Patients are asked to rate their intensity of sleep interference in the last 24 hours at the time of awakening on an 11-point scale from 0 (pain does not interfere with sleep) to 10 (pain completely interferes with sleep [could not sleep because of pain]).
- Patients’ global impression of change (PGIC): Patients are asked to rate their impression relative to baseline on a 7-point scale from 1 (greatly improved) to 7 (greatly worsened).
1 = greatly improved, 2 = improved, 3 = slightly improved, 4 = unchanged
5 = slightly worsened, 6 = worsened, 7 = greatly worsened
- Clinical global impression of change (CGIC): Investigators rate their impression relative to baseline on a 7-point scale from 1 (greatly improved) to 7 (greatly worsened).
1 = greatly improved, 2 = improved, 3 = slightly improved, 4 = unchanged
5 = slightly worsened, 6 = worsened, 7 = greatly worsened

6.3. Other endpoints

Not applicable.

6.4. Covariates

For safety and efficacy of Lyrica, no covariates or potential covariates are identified from clinical study data, etc. obtained to date.

7. Handling of missing data

If the seriousness/outcome of adverse events and action taken with Lyrica for the adverse events are missing, they will be handled as “unknown” at tabulation.

If body weight is not measured within the acceptable range at each time point (Appendix 1), it will be handled as missing and will not be imputed.

If data on efficacy evaluation (clinical efficacy) at Week 104 (or at discontinuation/completion of treatment) are missing, the data will be handled as missing even when the results of evaluation at Week 26, 52, or 78 are available. The missing data will not be imputed.

8. Statistical methods and statistical analyses

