Aiming at appropriate investigation of safety and efficacy of Lyrica during long-term use, the target sample size was set at 310, which is expected to have a 95% or higher probability to detect adverse reactions occurring at the incidence of 1% (0.97%) or higher in at least one patient.

A total of 310 patients with neuropathic pain who have been examined in the observation period of at least 52 weeks will be collected.

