4.1. Statistical hypothesis

Because this survey is not a confirmatory investigation, the testing should be considered as exploratory in nature. Unless otherwise specified, the 2-sided testing is performed with a significance level of 5%.

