8.1.3. Analysis of binary data

Frequency and its proportion will be calculated. If the confidence interval of proportion is calculated, a 2-sided 95% confidence interval (exact method) will be calculated.

If the proportion is compared between subgroups, Fisher’s exact test and Cochran-Armitage test (exact method) will be performed for the relationships with nominal scale data and

ordinal scale data, respectively, and the risk ratio and risk difference with their 95% confidence intervals will be calculated.

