8.2.3.4. Subgroup analysis

Number and proportion of patients with at least one adverse reaction will be tabulated by factor specified in Section 5.4. Furthermore, number and proportion of patients with at least one adverse reaction occurring (initial onset) at >13 to ≤52 weeks will be tabulated and tests

specified in Section 8.1.3 will be performed to evaluate the relationship between patient demographics, etc. and development of adverse reactions associated with long-term use. Risk ratio and risk difference for the incidence of adverse reactions and their 95% confidence intervals will be calculated between subgroups.

In addition, number and proportion of patients with adverse reactions in each subgroup will be tabulated by SOC and PT for factors showing a significant difference by testing to evaluate the relationship between patient demographics, etc. and development of adverse reactions. Moreover, patient demographics, etc. (including breakdown of past medical history and complications, prior and concomitant medications) will be tabulated in each subgroup and number and proportion of patients with serious adverse reactions will be tabulated by SOC and PT in each subgroup as necessary.

Laboratory parameters will be tabulated as specified in Section 8.2.3.3 in patients whose target disease is painful diabetic neuropathy.

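### Safety risk factors that overlap are each tested alone (SAP 8.2.3.4), so a crude result for one can be masked by, or borrowed from, another

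*SAP*

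**What the plan says.** - **Covariates.** SAP 6.4, covering safety and efficacy, says that "no covariates or potential covariates are identified from clinical study data, etc. obtained to date".
- **Factors.** SAP 5.4 lists 19 safety factors. They include two age groupings (three and six levels), renal impairment, creatinine clearance, hemodialysis, starting dose and maximum dose.
- **Tests.** In SAP 8.2.3.4, for reactions with first onset after week 13 and up to week 52, the tests "specified in Section 8.1.3 will be performed to evaluate the relationship between patient demographics, etc". SAP 8.1.3 defines them: "Fisher’s exact test and Cochran-Armitage test (exact method) will be performed for the relationships with nominal scale data and" ordinal data respectively, with risk ratios and risk differences. None is stratified or adjusted for another factor.
- **Links between factors.** SAP 8.2.3.1 counts clearance below 60 mL/min as renal impairment in the special-background tables. It also tabulates reactions in two clearance-by-dose groups: at least 60 mL/min starting on 150 mg, and a second group whose "creatinine clearance and the initial daily dosage are ≥ 30 to < 60 mL/min and 75 mg, respectively".
- **Further steps.** Factors found significant get descriptive tables (reactions by SOC and PT and, as needed, demographics and serious reactions). SAP 8.2.3.5 permits extra factor analyses without fixing any.
- **Status.** SAP 4.1: "Because this survey is not a confirmatory investigation, the testing should be considered as exploratory in nature".

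**The concern.** One-factor tests answer a clean question only when the factors are unrelated, or when nobody reads a factor's result as its own effect. Neither is safe here. SAP 8.2.3.4 gives its purpose as evaluating how patient characteristics relate to reactions in long-term use, and the renal, age and dose factors partly describe the same patients.

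Two errors follow. If patients with low clearance tend to start on less drug, a harmful effect of low clearance and a protective effect of the lower dose offset each other, and both crude ratios move towards 1. Conversely, a factor with no effect can look significant because it travels with one that has an effect. The descriptive follow-up in 8.2.3.4 starts only from a significant one-factor test, so a masked factor never triggers it.

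These are the only tests specified in the safety analysis, so the plan's statements about who is at higher risk rest on them.

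**Working it through.** **1. The plan's own figure.** SAP 2.1 sets 310 patients for a "95% or higher probability to detect adverse reactions occurring at the incidence of 1% (0.97%) or higher in at least one patient". Check: 1 − (1 − 0.0097)^310 = 0.951, and the smallest n is ln(0.05)/ln(0.9903) = 307.3, so 308. The figure reproduces. It concerns seeing one case and says nothing about comparing subgroups.

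**2. Assumed inputs.** The SAP gives no reaction rates, factor frequencies or overlap, so everything below is assumption except N = 310 and the two-sided 5% level (SAP 4.1). Dose and clearance are each cut in two. 65% of patients have clearance of at least 60 mL/min. The paired dose means the higher dose with clearance of at least 60 and the lower dose below 60.

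**3. Masking.** Reference risk 8% (odds 0.0870); higher dose and low clearance each double the odds. Odds of 0.1739 give a risk of 14.8%, and odds of 0.3478 give 25.8%. The dose risk ratio within strata is 0.148/0.080 = 1.85 (at least 60) and 0.258/0.148 = 1.74 (below 60).

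With 90% pairing the expected cells are:

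| Clearance | Dose | Patients | Events |
|---|---|---|---|
| ≥60 | higher | 181.4 | 26.9 |
| ≥60 | lower | 20.2 | 1.6 |
| <60 | lower | 97.7 | 14.5 |
| <60 | higher | 10.9 | 2.8 |

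Crude dose risk ratio = [(26.9 + 2.8)/192.2] / [(1.6 + 14.5)/117.8] = 0.154/0.137 = 1.13.

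| Pairing | Crude dose RR | Crude clearance RR |
|---|---|---|
| 100% | 1.00 | 1.00 |
| 90% | 1.13 | 1.13 |
| 80% | 1.27 | 1.26 |

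**4. Borrowing.** Now dose has no effect and low clearance doubles the odds. At a reference risk of 20%, the risk below 60 mL/min is 33.3%. With 90% pairing the crude higher-versus-lower dose risk ratio is [(181.4 × 0.20 + 10.9 × 0.333)/192.2] / [(20.2 × 0.20 + 97.7 × 0.333)/117.8] = 0.208/0.311 = 0.67, although the true ratio is 1. How often the dose test is significant (simulation, N = 310, 4,000 runs; Firth model with dose and clearance):

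| Reference risk | Pairing | Fisher, dose alone | Firth, adjusted |
|---|---|---|---|
| 20% | 80% | 31% | 5% |
| 20% | 90% | 49% | 5% |
| 8% | 80% | 16% | 5% |
| 8% | 90% | 28% | 4% |

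**5. A second set of assumptions.** N = 310, clearance below 60 in 30% of patients, and a second factor present in 80% of those and 30% of the rest. Fisher is compared with a two-factor logistic model (1,500 runs).
- Second factor null, reference risk 15%: falsely significant in 16%, 30% and 41% of crude tests at renal odds ratios of 2, 2.5 and 3, against about 5% adjusted. With 60% versus 30% overlap the crude rates are 9%, 14% and 19%. With no overlap both methods stay at about 4-5%, so the overlap is the cause.
- Opposing effects, reference risk 25%: power for the renal factor is 21%, 31% and 38% crude, against 57%, 76% and 89% adjusted.

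**6. What adjustment cannot do.** In the step 3 example about 46 events are expected. At 90% pairing the unpaired cells hold about 20 and 11 patients, and a two-term Firth model has about 21% power for dose (Fisher about 6%). At 80% pairing it is about 36% against 12%. At 100% pairing dose and clearance are collinear, and no model separates them.

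**The case against.** The best defence is that this is a descriptive survey. Testing is exploratory, SAP 4.2 sets no decision rule, and the sample size was never meant for factor comparisons. Crude ratios are valid descriptions of risk in each subgroup. SAP 8.2.3.1 tabulates reactions in elderly, pediatric, renally impaired and hepatically impaired patients with no significance trigger, and 8.2.3.5 leaves room for more. Adjustment also buys limited power (step 6).

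Much of this stands, and it limits the weight of the point. It does not remove the confounding: the 8.2.3.1 tables carry no test or adjustment, the clearance-by-dose table covers two cells, and 8.2.3.5 commits to nothing.

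A reader might infer more than the document supports:
- *The plan uses no covariate anywhere.* Not so. The pain-score analysis of covariance (8.1.1, 8.2.4.6) adjusts for the pre-treatment value, though not for other factors.
- *All these factors overlap by construction.* Only the two age groupings, and renal impairment with clearance, are documented. The dose-clearance link is implied by the two tabulated groups. Links of age or dialysis with clearance are plausible but not stated.
- *The only follow-up is a demographics table.* 8.2.3.4 also tabulates reactions by SOC and PT.
- *The crude results cannot be interpreted at all.* They can be read as subgroup risks, but not as separate effects.
- *6.4 misreports the earlier clinical data.* That cannot be judged from the SAP.

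**Conclusion.** The point holds as a weakness in interpreting the safety factor tests, not as an error in a confirmatory conclusion. Nineteen factors are tested singly, some overlap by the plan's own definitions, and no planned analysis adjusts one for another. Both masking and spurious association are possible.

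The size is conditional. With 310 patients, clearance doubling the odds and 80-90% pairing, a null dose factor is falsely significant in about 31-49% of crude tests (reference risk 20%) or 16-28% (8%), against about 5% adjusted. With equal and opposing effects, a within-stratum risk ratio of 1.74-1.85 shrinks to 1.13-1.27. If the overlap is weak, the problem is small. The reference risk, the odds ratios, the 65% share and the pairing are all assumptions, and the tested outcome may have fewer events than the example. An adjusted model beside the crude ratios is worth adding on those terms.

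**What to change.** **In SAP 8.2.3.4**, add one Firth logistic model for first adverse reaction after week 13 and up to week 52. Use coarsely grouped terms: one age variable, sex, one renal variable (for example creatinine clearance below 60 versus at least 60 mL/min), and starting daily dose. Use starting rather than maximum dose, because maximum dose is set after treatment begins and can be influenced by the reaction. Add target disease only if the number of events allows, with the grouping defined first. Report adjusted odds ratios beside the crude risk ratios whatever the one-factor tests show, with the numbers of patients and events used.

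**In SAP 6.4**, name these terms, and name the pre-treatment value already used as a covariate in 8.1.1.

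**Cost.** Some wording and one model, built from factors already in 5.4. Patients with missing clearance drop out, intervals will be wide, near-complete pairing of dose and clearance stays inseparable, and the results remain exploratory. The version history marks the survey as completed, so the model should be dated and fixed before its results are seen, and described as a late addition.
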